Specific Aim 1: The first specific aim is to demonstrate that spatial abilities are malleable in persons with DS. Uttal et al. (2013) conducted a meta-analysis on more than 200 spatial intervention studies in individuals of all ages demonstrating that abilities are highly malleable and that even limited experience in spatial tasks can produce positive and lasting effects in TD children and adults. Indeed, numerous studies have shown that spatial ability performance of TD children and adults can be achieved by providing experience with tasks that utilize spatial abilities and do not require direct instruction (e.g., block play and puzzle construction). It is reasonable to expect that these results will generalize to persons with DS. However, this needs to be empirically evaluated. Hence, one important goal of the proposed research is to demonstrate that experience with spatial tasks can promote improvement in two specific spatial abilities (mental rotation and perspective taking) in persons with DS. To test this specific aim, we will compare spatial ability performance of persons with DS before and after varying levels of experience with spatial activities.

Specific Aim 2: The second specific aim is to evaluate whether persons with DS and TD children matched on nonverbal ability exhibit the same degree of improvement as a function of similar experience with spatial abilities. If persons with DS exhibit greater improvement than TD children, then it may be that the weaknesses observed in spatial abilities reflect a lack of opportunity to engage in spatial ability experience. If, on the other hand, persons with DS exhibit less improvement, it may be that weaknesses observed in spatial abilities reflect a lesser ability to benefit from intentional experiences. In the proposed research, we will also evaluate the relations between degree of improvement and measures of Nonverbal ability, Receptive Language, and Chronological Age to identify differences in how these variables contribute to performance improvements in the two groups. The results of these analyses may also help to identify persons with DS who are most likely to benefit from spatial ability experience to promote improvements in spatial abilities.

c) **Describe the study design (e.g., single/double blind, parallel, crossover, control, experimental, observational, etc.)**

N/A

Single blind

Double blind

Parallel

Crossover

Control group

Experimental group

Observational

Other

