Mental Rotation Assessment - On each trial, participants will be presented a geometric shape (e.g., a block letter L) in the center of a computer screen that completes one of two rectangles presented at the bottom of the same screen. The open area in one rectangle is the mirror image of the open area in the second rectangle. The shape in the center of the screen will fit one of the rectangles when horizontal. The shape can be rotated from horizontal by 0, 45, 90, 135, 180, 225, 270, or 315 degrees. Participants respond by touching the rectangle into which the shape will fit once oriented properly (using touchscreen technology). Participants receive 4 trials at each orientation.

Perspective Taking - Participants will be seated at a table with four chairs and four different objects (street lamp, mailbox, stop sign, traffic signal) representing each location on the corner of a city block in front of each chair. A stuffed animal is placed behind each object. One experimenter walks around the table stopping at each location. At each location, the participant is told that the experimenter is taking a picture from that location and he/she is asked to look at four pictures. The task is to select the picture that the experimenter has just taken. The four pictures consist of the participant's point of view, a mirror image of the participant's point of view, the experimenter's point of view, and a mirror image of the experimenter's

Due to CoVid Restrictions, Procedures were adapted for online presentation via Zoom. Ravens and PPVT-4 used available commercial formats. Mental Rotation and Perspective Taking involved the creation of Video presentations. Online presentation was approved by the University IRB on 03/04/2020.

point of view. This task will take 5 - 10 minutes.

Assessments 2 and 3 will include only Mental Rotation and Perspective Taking Assessments.

Spatial Ability Experience will include two tasks of Object manipulation and two Large Environment Experiences. These tasks are meant to provide experience.

Object Manipulation Experience: Two categories of tasks will be used to provide object manipulation experience: LEGO Block Play and Puzzle Construction. One task will be used in each spatial ability experience, with tasks alternating between sessions.

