Specific Aim 1 evaluates the malleability of MR and PT performance in participants with DS. Consistent with Aim 1, we will apply Multivariate ANOVA to the subsample of DS children. If the test for sphericity is significant, we will interpret the multivariate tests for the within subject effects. If not, we will use the univariate tests due to their increased statistical power. With either option, the test for the effect of Assessment, if significant, would indicate that performance of the DS children improves over time. We will then evaluate the interaction of AssessmentDelay, which if significant would signify that Delay vs No Delay participants exhibit a different magnitude of improvement across Assessment times. One contrast of interest compares Delay vs No Delay participants at Assessment 2. Performance favoring the No Delay participants would indicate a significant effect of spatial ability experience. A second contrast of interest compares Assessment 3 performance to Assessments 1 and 2 for the Delay participants. If we are able to confirm that the Delay participants exhibit higher scores at Assessment 3 than at Assessments 1 and 2 (which should not differ) then the benefits of spatial ability experience for persons with DS would be further confirmed.

Specific Aim 2 evaluates possible differences in rate and magnitude of improvement of DS and TD participants. We will approach Aim 2 in a very similar statistical manner. For Aim 2a, we will apply Multivariate ANOVA to the whole sample to test for the effect of AssessmentGroup. If significant, it is indicative that DS and TD participants do not exhibit the same degree of improvement following training. If improvement in performance is greater for the participants with DS, it

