would indicate that experience may be a primary contributor to initial differences in spatial abilities of the DS and TD participants. If improvements are greater for TD children or similar for both groups, it would suggest that initial differences in spatial abilities between groups are not solely due to differences in experience. We will also examine the interaction of Assessment Group Delay complemented with contrasts to explore more closely how participants with DS compare to TD children. For example, we will compare rate of change over Assessments to see if the participants with DS need more experience to reach the same level of performance as the TD children. This may indicate the need for more intensive training for participants with DS to modify spatial ability performance.

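### Aim 2 reads the direction of the DS–TD difference in gain as a clue to why DS participants start lower, but starting level alone can create or reverse that difference, and no measure of prior spatial experience is listed

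*Combined protocol and SAP*

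**What the plan says.** Section 3(d), Data analysis, sets the Aim 2 test: "we will apply Multivariate ANOVA to the whole sample to test for the effect of AssessmentGroup" (the interaction sign between the two factor names is lost in the text). No baseline adjustment, transformation, or floor or ceiling handling is stated.

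The direction of the interaction is then interpreted. If DS participants improve more, section 3(d) says this "would indicate that experience may be a primary contributor to initial differences in spatial abilities of the DS and TD participants". If TD children improve more, or the groups improve alike, it concludes that experience is not the whole explanation. Section 2(b), Specific Aim 2, gives the same reading of a greater DS gain, "it may be that the weaknesses observed in spatial abilities reflect a lack of opportunity to engage in spatial ability experience", and takes a smaller DS gain as possibly showing a lesser ability to benefit.

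The tasks are described in section 3(b):

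- Mental rotation offers two rectangles: "Participants respond by touching the rectangle into which the shape will fit once oriented properly". "The shape can be rotated from horizontal by 0, 45, 90, 135, 180, 225, 270, or 315 degrees", and "Participants receive 4 trials at each orientation".
- Perspective taking offers four pictures: "The task is to select the picture that the experimenter has just taken". The number of trials is not given.

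The groups are matched on nonverbal raw score (section 3(b), Ravens 2), not on spatial score. The lay summary in 2(a), and Section 2, item 1, of the part on cognitively impaired persons, presume weaker spatial ability in DS. The first assessment consists of a nonverbal test, a vocabulary test and the two spatial tasks. Section 2(b) relates improvement only to nonverbal ability, receptive language and age.

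**The concern.** The interpretive rule has something to explain only when DS participants start below TD children. On a bounded score, that is also when raw gains stop being comparable. A group near the ceiling has little room to move, and a group near chance shows little of whatever it has gained. The sign of Assessment x Group can therefore reflect where the groups start rather than how they respond.

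A second gap does not depend on scoring. Response to 32 experience sessions shows what those sessions did. It does not show whether the earlier deficit came from lack of opportunity, because no measure of earlier spatial experience is listed for either group.

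At stake is the explanatory half of Aim 2: lack of opportunity versus lesser ability to benefit. The DS-only Delay comparison in Aim 1 is not affected.

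**Working it through.** **The plan's own figure.** The section on research involving children gives a detectable f(V) of .27 for 4 groups x 3 repetitions, alpha .05, power .80, N = 96. With lambda = 0.27² x 96 x 2 = 14.0 and 6 and 184 degrees of freedom, power is 0.797, so the figure reproduces. It says nothing about starting level.

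**Inputs from the document.** Mental rotation has 8 orientations x 4 trials = 32 trials with two choices, so chance g = 1/2. Perspective taking has four choices, so nominal g = 1/4.

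**Assumed inputs.** Scoring as accuracy, the starting levels and the size of the gain are not given.

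**Step 1: the same latent gain at different starts.** Accuracy is p = g + (1 − g) x logistic(theta), so theta = ln[(p − g)/(1 − p)]. Add 0.6 to theta in both groups, with g = 1/2:

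| Start | theta | theta + 0.6 | End | Gain (points) |
|---|---|---|---|---|
| 55% | ln(0.05/0.45) = −2.197 | −1.597 | 58.4% | 3.4 |
| 65% | ln(0.15/0.35) = −0.847 | −0.247 | 71.9% | 6.9 |
| 80% | ln(0.30/0.20) = 0.405 | 1.005 | 86.6% | 6.6 |
| 90% | ln(0.40/0.10) = 1.386 | 1.986 | 94.0% | 4.0 |

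Pairing the rows as DS/TD:

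- 65%/90%: 6.9 vs 4.0, so DS looks 6.9/4.0 = 1.7 times as responsive.
- 55%/80%: 3.4 vs 6.6, so DS looks about half as responsive (3.4/6.6 = 0.52).
- 65%/80%: 6.9 vs 6.6, almost no difference.

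**Step 2: the planned test.** The multivariate Assessment x Group test was simulated (2,000 replicates) with identical latent gain in both groups, an assumed person SD of 0.8 log-odds and planned cells of 4 x 24. Figures in brackets use 30 DS and 54 TD, the numbers consented, split evenly over Delay by assumption.

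| Task | DS/TD start | Latent gain | Significant result |
|---|---|---|---|
| Mental rotation | .70/.90 | 1.2 | DS greater 69% (64%) |
| Mental rotation | .70/.90 | 0.7 | DS greater 21% (22%) |
| Mental rotation | .55/.70 | 1.2 | TD greater 36% (31%) |
| Mental rotation | .55/.70 | 0.7 | TD greater 18% (18%) |
| Mental rotation | .60/.80 | 0.7 or 1.2 | either direction 5.6–6.2% (8.3–8.5%) |
| Perspective taking, 16 trials assumed | .60/.90 | 0.7 or 1.2 | DS greater 38–87% (40–84%) |
| Perspective taking, 4 trials assumed | .60/.90 | 0.7 or 1.2 | DS greater 14–34% (17–38%) |

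With equal starting levels and planned cells, total rejection was 4.7–5.8%. The excess above 5% therefore comes from starting level.

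**Step 3: which decision rule protects.** This simulation used mental rotation, 30 DS and 54 TD, and an identical latent gain of 0.6. False claims of a different raw gain were 17.5% at 65%/90% and 18.7% at 55%/80%. Requiring only that the log-odds difference have the same sign left 17.5% and 18.5%. Requiring the guessing-corrected log-odds interaction to be significant as well cut them to about 2–3%. The exact rates depend on the assumed spread and test; the contrast between the rules is the point.

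**The case against.** The strongest reply is that Aim 2 is largely descriptive. It asks whether the groups improve to the same degree and whether experience narrows the gap. Raw Assessment x Group is a legitimate answer to that, and section 3(d) also looks at whether DS participants reach the TD level. This stands: the test may stay, and the objection is to what is inferred from its sign.

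A reader might infer that the plan claims lack of experience caused the deficit. It does not. Both sections are hedged, and the contrary branch says only that experience is not the sole source. The hedge weakens the claim but leaves out the rival explanation through starting level.

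A reader might also infer that the artefact must be present and large. The document does not support that either. No baseline scores are given, TD children are aged 4 to 9 and matched on nonverbal ability, and a TD start of 90% is not established. At some plausible starts the artefact nearly vanishes.

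Nor does the document show that prior experience was never measured. It lists no such measure, but the grant proposal named among the attachments was not available. Accuracy scoring is likewise an assumption, though a natural one for a fixed number of forced-choice trials; a response-time score would raise different scale questions.

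**Conclusion.** The concern holds as a limit on interpretation. As written, the rule can point to lack of opportunity, or to lesser ability to benefit, when both groups respond identically. The effect runs from almost nothing (6.9 vs 6.6 points; 5.6–6.2% rejection in mid-scale with planned cells) to dominant (69% false DS-greater results for mental rotation at .70/.90 with a gain of 1.2), and its direction can reverse. These sizes rest on accuracy scoring and on assumed baselines, gains and person spread. The other limb needs none of those assumptions: without a measure of prior experience, a genuine difference in gain still does not identify the source of the initial difference. The matter should be addressed before Aim 2 is reported.

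**What to change.** 1. In sections 2(b) and 3(d), replace the explanatory sentences with a statement that DS participants gained more, or less, than TD children from the same experience, and add that this does not identify the cause of the initial difference.
2. State how each task is scored. Report, by group, how many participants were at or near chance and how many at ceiling at Assessment 1.
3. Add a sensitivity analysis of Assessment x Group on a guessing-corrected log-odds scale, from trial-level data if kept and from number correct otherwise. Use guessing of 1/2 for mental rotation. For perspective taking, vary it around 1/4, because the wrong pictures include the participant's own view and a participant who picks that view can score below chance.
4. Call one group more responsive only if the interaction is significant in the same direction on both the raw and the log-odds scale. Agreement in sign alone is not enough.

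The continuing review form reports data collection complete and analysis underway, and none of this needs new data. The cost is wording, a small table and one extra model per task. The price is a weaker explanatory statement and some loss of power for the stronger claim.

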c) Provide stopping rules for the study. If the proposed study is a clinical trial where a drug, vaccine, device or other treatment is compared to a placebo group or comparison treatment group, what are the guidelines or endpoints by which early decisions regarding efficacy or lack of efficacy can be made? For example, it may be reasonable to stop enrollment on a study when efficacy has already been clearly demonstrated, to avoid unnecessary enrollments of additional participants. Alternatively, it may be reasonable to stop enrollment when it is clear that efficacy will never be demonstrated, given the statistical power of the study as designed. Describe the guidelines that are in place to assist in making these determinations, if relevant to the proposed study.

NA

d) Describe how data analysis will be performed (statistical tests, methods of evaluating data) and indicate the smallest group/unit for which separate reporting will occur. For studies involving a questionnaire, if data and reliability information are available, please describe or provide references. (Page numbers from a sponsor's protocol/grant may be referenced in this section).

The independent variables of interest will be Group (DS and TD), Delay (No Delay and Delay), and Assessment (1, 2, and 3). The smallest number of participants in any given cell of the design is 20 participants.

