*** * * Subject Population(a-h) * * ***

7. Subject Population - In the space below, please detail the participants that you are requesting to recruit (include description of each group requested)

a) Expected age range of participants. (For example - 19 yrs to 90 yrs).

Participants with Down syndrome will be between 10 and 30 years of age.

Typically developing children will be between 4 and 9 years of age.

We will test 48 participants per group - plus an additional 6 typically developing children as needed to provide a closer match on nonverbal ability for the children in the Experimental condition with the children in the control condition.

b) i) Number to be directly solicited for this research.
 
ii) Number to be consented (including withdrawals or screen failures)
 
iii) Number expected to complete the study.
 
c) If this is multi-center study, number of participants to complete the study study-wide
 
d) If study involves review of medical or other records, number of records to be reviewed.
 
e) If women, minorities, or minors are excluded, a clear compelling rationale must be provided unless not applicable. Examples for not including minors: disease does not occur in children; drug or device would interfere with normal growth and development; etc.
 
f) Describe how potential participants will be identified for recruitment (e.g., chart review, referral from individual's treating physician, those individuals answering an ad). How will potential participants learn about the research, and how will they be recruited (e.g., flyer, e-mail, web posting, telephone, etc.)? State where recruitment materials will be located. Click "Add" to upload recruitment materials document.
	
X N/A
 
N/A
 
102
 
102
 
N/A
 
102
 
X N/A
 
NA

--	--

Important to remember: Study Activities cannot begin until IRB approval is granted.

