The children used in this study are necessary for providing a comparison group matched on non-verbal ability with participants with Down syndrome. In this type of research, it is necessary to evaluate the performance of individuals with Down syndrome against participants who are matched on general ability measures to determine if the difficulties associated with Down syndrome are beyond that which would be expected based on developmental level.

b) Has this research been conducted in adults? Y

If yes, is there any indication that the proposed research would benefit, or at least not be harmful to children?

Similar research has been conducted in adults and children with no adverse effects. The children are essential for providing a comparison group for the participants with Down syndrome.

c) Indicate how many children you propose to enroll in the study and justify this number (whenever possible, involve the fewest number of children necessary to obtain statistically significant data which will contribute to a meaningful analysis relative to the purpose of the study).

All of the typically developing participants will be children (48 participants originally planned). Many of the participants with Down syndrome will also be participants (we anticipate about half of the 48 participants in this group, or 24). The total number of participants was determined by power analysis. A 4 groups x 3 repetitions analysis with alpha set at .05, power set at .80, and total N = 96 (24 in each group) would be sufficient to observe a significant effect size (f(V)) of .27 or greater. To evaluate the power for simple effects tests to compare the effects of training for the DS and TD participants separately, we conducted a 2 groups (Delay and No Delay) x 3 repetitions analysis with alpha set at .05, power set at .80, and total N = 48 (24 in each group). Power analysis indicated that 48 total participants would be sufficient to observe a significant effect for effect sizes (f(V)) of .27 or greater for main effects of Delay and of .25 or greater for main effects of Assessment Time. Power calculations were conducted in GPower 3.1.9.2 (Faul et al., 2007). However, we are requesting an additional 6 typically developing participants at this time to make it possible to better match the Experimental and Control group children on nonverbal ability.

d) Describe how assent of a child will be obtained and documented (if applicable). If not applicable, explain why.

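### Aim 2 gives similar improvement in the DS and TD groups an explanatory meaning, but sets no margin or interval for it, so only a non-significant Assessment x Group test can lead there

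*Combined protocol and SAP*

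**What the plan says.** Section 3(d), on data analysis, tests Aim 2a through the Assessment x Group effect in a multivariate ANOVA on the whole sample. Its meaning is stated for one outcome: "If significant, it is indicative that DS and TD participants do not exhibit the same degree of improvement following training".

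The section then interprets the direction of the result. Greater improvement in the DS group is taken to point to experience as a main contributor to the initial gap. The other outcomes share one reading: "If improvements are greater for TD children or similar for both groups, it would suggest that initial differences in spatial abilities between groups" are not explained by experience alone. Further contrasts follow, including the three-way interaction with Delay and a comparison of rates of change.

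The power statement is in Subject Population(m), Section 2(c): "A 4 groups x 3 repetitions analysis with alpha set at .05, power set at .80", "total N = 96 (24 in each group"), which "would be sufficient to observe a significant effect size (f(V)) of .27 or greater". For each diagnostic group separately, the detectable effects are given as f(V) "of .27 or greater for main effects of Delay and of .25 or greater for main effects of Assessment Time". No power is stated for the DS versus TD comparison of improvement.

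**The concern.** Whether the two groups improve equally is the question that Aim 2 poses in section 2(b). The plan tests for a difference and has no method that could support sameness. Nothing in the documents says how close the two improvements must be to count as similar, and the added contrasts supply no criterion either.

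That leaves a non-significant interaction as the only working route to the similar branch. The plan gives that branch the same reading as a demonstrated TD advantage. An inconclusive comparison could therefore be reported as evidence about why people with DS have spatial weaknesses, when the data were still compatible with a DS advantage, which the plan would read the opposite way.

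**Working it through.** **Inputs from the documents.** Alpha is 0.05, power 0.80 and total N 96 (Subject Population(m), Section 2(c)). For allocation, Subject Population(a-h), item 7(a), says "We will test 48 participants per group", with up to six extra TD children. Consented numbers are 30 DS and 54 TD (Continuing Review, item 5).

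**Not in the documents.** The DS-TD effect, the SD and the correlation between assessments are not given. Assumption: a true DS advantage d of 0.3 to 0.5, in units of the SD of change.

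**1. The plan's own figure.** For the 4 x 3 within-between interaction (Pillai trace, s = 2, df 6 and 184), the noncentrality is λ = N × s × f(V)² = 96 × 2 × 0.27² = 14.0. Power is 0.797, and exactly 0.80 needs f(V) = 0.271. The stated 0.27 reproduces.

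**2. What that figure covers.** It applies to a 6-df test across the four Group x Delay cells. The DS-TD test on one outcome has 2 df. At N = 96 and the same f(V), λ = 96 × 0.27² = 7.0 and power is 0.64. For 80% power the 2-df test needs f(V) = 0.322. With equal groups d = 2f, so this is d = 0.64.

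**3. Chance of missing a true DS advantage.** λ = d² × n1n2/(n1 + n2).
- Planned: 48 × 48/96 = 24, so λ = 6.00 at d = 0.5.
- Consented: 30 × 54/84 = 19.29, so λ = 4.82 at d = 0.5.

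The 1-df column is a two-sided comparison of change scores, F(1, N − 2). The 2-df column is Assessment x Group with the four cells in the model, F(2, N − 5). Entries are 1 minus noncentral-F power.

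| d (SD of change) | 48 v 48, 1 df | 48 v 48, 2 df | 30 v 54, 1 df | 30 v 54, 2 df |
|---|---|---|---|---|
| 0.3 | 69% | 77% | 74% | 81% |
| 0.4 | 51% | 61% | 59% | 68% |
| 0.5 | 32% | 43% | 42% | 53% |

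With the six extra TD children (48 v 54), the misses at d = 0.5 are 30% and 40%.

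**4. Width of the interval.** Half-width = t × √(1/n1 + 1/n2).
- Planned: 1.986 × 0.204 = 0.405 SD.
- Consented: 1.989 × 0.228 = 0.453 SD.

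In the consented sample, an observed DS advantage of 0.20 SD would be non-significant on the change contrast, with a 95% CI from 0.20 − 0.45 = −0.25 to 0.20 + 0.45 = 0.65. That interval does not show similarity.

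**5. Sensitivity to scale.** With equal variances, SD of change = raw SD × √(2(1 − r)). The two scales coincide at r = 0.5. At r = 0.7, a raw advantage of 0.5 SD equals 0.5/√0.6 = 0.65 SD of change. If the advantage is halved at Assessment 2, when the Delay half has had no experience, 2-df power is 0.802 at 48 v 48 and 0.702 at 30 v 54, so misses fall to 20% and 30%. At r = 0.8 power is 0.937 and 0.872, giving misses of 6% and 13%.

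**6. Power to show similarity.** For an equivalence test with an assumed margin of 0.5 SD of change, one-sided 0.05 on each side and no true difference, power is about 58% at 48 v 48 and 42% at 30 v 54. For 80% power about 69 per group are needed.

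**The case against.** The strongest reply is that the plan nowhere says a non-significant test means similar improvement. It states only what significance indicates, and section 2(b) interprets greater and lesser improvement with no similar branch. The data-analysis field is part of an ethics form that allows reference to the grant, which is attached but not available here and might say more. All of this is fair. The published text nevertheless contains a similar branch, gives it a meaning and offers no other way to reach it.

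Three stronger readings are tempting, and the documents do not support them.

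- **The trial would miss a moderate DS advantage more often than not.** At 0.5 SD of change this fails at the planned size (32% to 43%). At the consented size it holds only for the 2-df test (53%), not for the change contrast (42%). Both figures depend on a scale that the documents do not fix.
- **The plan draws a causal conclusion.** The wording is hedged and argues only against experience as the sole explanation.
- **Assessment x Group is the only comparison planned.** Section 3(d) adds the three-way interaction and further contrasts, although none defines similarity.

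There is also a practical objection. Continuing Review, item 13, says that data collection is complete and analysis is in progress, so a margin may no longer be fixable in advance. That stands, and it limits the remedy.

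**Conclusion.** The concern holds as a fault in the interpretation rule. Similar improvement has no criterion, is reached in practice through non-significance, and is then read like a TD advantage. This does not depend on any particular power figure, because non-significance does not show similarity at any of the powers calculated.

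The size does depend on assumptions. In SD-of-change units, a true DS advantage of 0.5 SD is missed in 32% to 43% of trials as planned and 42% to 53% in the consented sample. At 0.3 SD the misses are 69% to 77% and 74% to 81%. High correlation between assessments with effects on the raw-score scale lowers these rates substantially. The consented numbers are an upper limit on the sample analysed if any participant lacks a later assessment.

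**What to change.** Revise the Aim 2 interpretation in section 3(d) as follows.

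- For mental rotation and for perspective taking, report the DS minus TD difference in improvement with its 95% CI, naming the assessments between which improvement is measured.
- Separate the similar outcome from the TD-advantage outcome, and do not read a non-significant interaction as similarity.
- Where the CI still includes a meaningful DS advantage, call the result inconclusive and draw no inference about the role of experience.
- Use the word similar only if the whole CI lies within a margin fixed before anyone has seen the group comparison. If the comparison has already been seen, report the CI alone.

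The cost is a change of wording and one interval per ability, with no new data. The drawback is that the conclusion will more often be inconclusive. With half-widths of about 0.41 to 0.45 SD of change, any margin narrower than the half-width puts a finding of similarity out of reach.

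### Aim 2 reads similar improvement in the two groups as evidence about the cause of the initial DS-TD gap, without first requiring that the experience changed performance

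*Combined protocol and SAP*

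**What the plan says.** Specific Aim 2 (item 2(b)) asks whether DS and TD participants "exhibit the same degree of improvement as a function of similar experience with spatial abilities". The analysis in item 3(d) is: "we will apply Multivariate ANOVA to the whole sample to test for the effect of AssessmentGroup". This uses both arms of each group together.

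Item 3(d) attaches these readings:

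- A significant result: "it is indicative that DS and TD participants do not exhibit the same degree of improvement following training".
- DS improve more: this "would indicate that experience may be a primary contributor to initial differences in spatial abilities of the DS and TD participants".
- All else: "If improvements are greater for TD children or similar for both groups, it would suggest that initial differences in spatial abilities between groups" are not explained by experience alone.

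The plan gives no margin for what counts as similar and states no efficacy condition for the third reading.

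The plan does test whether experience works. Under Aim 1 it examines Assessment x Delay and compares Delay with No Delay at Assessment 2, within the DS subsample. Under Aim 2 it adds the Assessment x Group x Delay interaction with contrasts. Item 2(d) makes the Delay arm the control for practice on the measures. None of these results is made a condition for the Aim 2 reading.

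**The concern.** Change across three assessments mixes training gain with retest gain, and part of the Delay arm's change comes before any training. If the sessions do nothing and both groups gain equally from repeated testing, improvement is similar, and the stated rule still yields a conclusion about why the groups differed at the start. A programme that moved nobody carries no information on whether past lack of experience caused the deficit.

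This is not only a matter of power. An equivalence margin would not cure it, because two null training effects really are equivalent. The three-way interaction would not cure it either, because two null training effects also show no three-way difference. At stake is that a failed intervention could be reported as evidence about the origin of spatial weakness in Down syndrome.

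**Working it through.** **Inputs from the protocol.** Alpha .05 and power .80 come from the power statement under Research Involving Children, Section 2(c): "A 4 groups x 3 repetitions analysis with alpha set at .05, power set at .80". Item 3(d) gives no other level. Planned N is 96, 24 per cell. The Continuing Review form (item 5) records 54 children and 30 participants with DS as consented. There are two outcomes, mental rotation and perspective taking.

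**The plan's own figure first.** The statement says that "total N = 96 (24 in each group) would be sufficient" "to observe a significant effect size (f(V)) of .27 or greater". For the 4-group by 3-assessment multivariate interaction, df1 = 6, df2 = 184 and noncentrality = f(V)² x N x s with s = 2:

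- .27² x 96 x 2 = 14.0, which gives power .797. The figure reproduces (detectable f(V) = .271).
- It belongs to the 4-group interaction. The 2-group Assessment x Group test behind Aim 2 has df 2 and 91 and noncentrality .27² x 96 = 7.0, so power is about 64%. A real group difference can therefore also land in the similar branch. That is a separate matter from this point.

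**Inert programme, equal retest gains (assumed).** There is then no Assessment x Group effect, so for one outcome:

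- P(similar, read as not significant) = 1 - .05 = .95
- P(significant, TD greater) = .05/2 = .025
- P(TD greater or similar) = .95 + .025 = **.975**

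Simulation with the plan's sphericity-dependent choice of test gives 97.4-97.6% at 48 v 48, and 97.5% at 48 v 54 and at 30 v 54. For two independent outcomes, .975² = 95.1% that both give the reading.

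**Experience works equally in both groups.** Adding 0.5 or 0.8 SD to both again leaves no Assessment x Group effect. Simulation gives 97.1-97.9%. The branch is reached equally often whether the programme works or not.

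**Inert programme, unequal retest gains.** Assumed: correlation .5, with the gain rising evenly to the stated total by Assessment 3.

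| Retest gain | TD greater or similar, 48 v 48 | 30 v 54 |
|---|---|---|
| DS only, 0.3 SD | 76% | 81% |
| DS only, 0.5 SD | 43% | 53% |
| TD only, 0.3 SD | 99.9% | 99.8% |

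In the second row the remaining 57% and 47% of trials give the DS-greater reading, which credits experience with the initial gap although only practice was at work.

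**Adding a condition.** Require No Delay to exceed Delay at Assessment 2 in the whole sample, adjusted for Assessment 1, Group in the model, two-sided .05. Under an inert programme it passes about .025 of the time, so similar improvement is read causally in about .95 x .025 = 2.4% of trials. Pass rates at 30 v 54, correlation .5 to .8:

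| True effect of experience | Condition passes |
|---|---|
| 0.5 SD in both groups | 74-97% |
| 0.5 SD in DS only | about 14-26% |
| 0.5 SD in TD only | about 38-66% |

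**The case against.** **The 97.5% is not a property of this trial.** This is right. It is 1 - alpha/2 for any two-sided .05 test with no group difference, whatever the sample size or correlation. Its value here is to show that the branch does not discriminate.

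**A reader might infer that any ineffective programme gives this conclusion about 97% of the time.** The documents do not support that. They give no retest gains. The age ranges in item 7(a), 10 to 30 years for DS and 4 to 9 for TD, give no reason to assume equal ones, and the second table row shows how far the figure can move.

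**A reader might also infer that the plan never checks whether experience works.** It does, in Aim 1 for DS and through the three-way interaction. An inert programme would probably show as null there, next to the Aim 2 result. The wording is also hedged, the plan does not literally equate non-significance with similarity, and talk of improvement after training can be taken to presuppose that training helped. Item 2(b) interprets only greater or lesser improvement. What stands is that no sentence links the efficacy result to the reading of similar improvement.

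**A condition on every Aim 2 reading would do harm.** This also stands. A whole-sample condition would often block a true effect confined to one group, which is the kind of pattern Aim 2 exists to find.

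**Conclusion.** The point holds for the similar reading. As written, item 3(d) draws an inference about the source of the initial DS-TD difference from similar improvement, whether or not experience had any effect. Under equal retest gains, which is an assumption, TD greater or similar arises with probability 97.5% per outcome, both for an inert programme and for one that works equally in both groups. Under unequal gains the probability differs, and practice alone can lead to the opposite reading. The defect is a missing link between two planned results. It is not a missing test, and it does not justify restricting all of Aim 2. It should be corrected, since the rule followed literally can give an unsupported causal conclusion.

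**What to change.** In item 3(d), after the Aim 2 readings, add:

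> Similar improvement will be read as evidence about the source of initial DS-TD differences only if No Delay exceeds Delay at Assessment 2 in the whole sample (adjusted for Assessment 1, p < .05), separately for mental rotation and perspective taking; otherwise it will be reported as uninformative on that question.

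Do not apply this condition to the DS-greater or TD-greater readings. Report those beside the No Delay v Delay contrast within each group and the Assessment x Group x Delay interaction already planned. That also lets a reader see when a group difference may be practice alone.

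**Cost.** No new data are needed. The whole-sample adjusted contrast is a small new analysis, because the planned Assessment 2 contrast is stated for the DS subsample with no adjustment mentioned. The Continuing Review form (item 13) says data collection is complete and analysis has begun, so the sentence should be dated as added after data collection ended. At 30 v 54, a true 0.5 SD effect in both groups would be missed, and similar improvement reported as uninformative, in about 3-26% of trials, depending on the correlation between assessments.
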